### 10.2.3 Safety analysis

Safety analyses will be based on all biopsied subjects. Only AEs related to the biopsies will be reported. Safety data will be summarized using descriptive statistics. Categorical

variables will be summarized by number and percentage. Continuous variables will be summarized using n (number of subjects with available data), mean, standard deviation, median, upper and lower quartiles, and range (minimum and maximum), unless otherwise specified.

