## 7 TOXICITIES AND DOSEAGE MODIFICATION

Because all drugs are FDA-approved for this indication and are being prescribed consistent with their label, the only AEs collected will be those related to the biopsy. Dose modifications will be at the discretion of prescribing physician based on standard practice.

This study will utilize the CTCAE (NCI Common Terminology Criteria for Adverse Events) Version 5.0 for adverse event and serious adverse event reporting. A copy of the CTCAE Version 5.0 can be downloaded: (<http://safetyprofiler-ctep.nci.nih.gov/CTC/CTC.aspx>).

All supportive measures consistent with optimal patient care will be given throughout the study.

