## 9.2 Safety

Routine safety and tolerability will be evaluated from the results of reported signs and symptoms, scheduled physical examinations, vital sign measurements, and clinical laboratory test results. More frequent safety evaluations may be performed if clinically indicated or at the discretion of the investigator.

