## 10.2 Statistical Analysis

### 10.2.1 Primary Endpoint

#### **Progression Free Survival (PFS)**

PFS is defined as the time from the time results are given to the treating oncologist to the first occurrence of disease progression or death from any cause (whichever occurs first) according to RECIST 1.1. Patients without disease progression or death at the time of analysis will be censored at the last disease assessment date from their last evaluable RECIST v1.1 assessment.

For the primary objective, all enrolled patients who receive therapy concordant with the genomic recommendation will be evaluable for analysis. Concordant therapy will be any anti-estrogen plus any PI3K inhibitor in the “fulvestrant plus alpelisib” group, any anti-estrogen plus any MTOR inhibitor in the “exemestane plus everolimus” group, any antiestrogen in the “fulvestrant” group, and any cytotoxic chemotherapy in the “capecitabine” group.

The PFS curve will be estimated using the Kaplan-Meier product-limit method. Two-sided, 95% CI for the median PFS will be computed by the Brookmeyer and Crowley method with log-log transformation.

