#### 14.3.2 Serious Adverse Event (SAE)

Information about all serious adverse events within 30 days of a study biopsy will be collected and recorded. A serious adverse event is an undesirable sign, symptom, or medical condition which:

- is fatal or life-threatening
- results in persistent or significant disability/incapacity
- is medically significant, i.e., defined as an event that jeopardizes the patient or may require medical or surgical intervention to prevent one of the outcomes listed above
- causes congenital anomaly or birth defect
- requires inpatient hospitalization or prolongation of existing hospitalization, unless hospitalization is for:
  - routine treatment or monitoring of the studied indication, not associated with any deterioration in condition (procedures such as central line placements, paracentesis, pain control)
  - elective or pre-planned treatment for a pre-existing condition that is unrelated to the indication under study and has not worsened since the start of study drug
  - treatment on an emergency outpatient basis for an event not fulfilling any of the definitions of a SAE given above and not resulting in hospital admission
  - social reasons and respite care in the absence of any deterioration in the patient's general condition

Adverse events which fall within the definitions listed above must be reported as an SAE regardless, if they are felt to be related or not.

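### Section 10.2.3 limits the safety analysis to biopsy-related AEs and so omits SAEs collected regardless of cause; Sections 9.2 and 14.3.1 also conflict with the plan's stated scope

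*Combined protocol and SAP*

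**What the plan says.** Three statements set a narrow scope and agree with each other:

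- Section 7, citing approved drugs used according to label, says "the only AEs collected will be those related to the biopsy".
- Section 10.2.3 bases the safety analysis on everyone biopsied and adds "Only AEs related to the biopsies will be reported".
- One sentence of Section 14.3.1 restricts AE collection to events related to the study biopsies.

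Other text goes wider:

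- Section 14.3.2: "Information about all serious adverse events within 30 days of a study biopsy will be collected and recorded". Events meeting the SAE definition "must be reported as an SAE regardless, if they are felt to be related or not".
- Section 14.4 sends SAEs to the DSMC and IRB, and the Data and Safety Monitoring Plan in Section 14.2 has the DSMC review all of them.
- The paragraph of Section 14.3.1 that follows the restriction says that information on all AEs, however detected, is collected and recorded. The same section defines an AE as arising after study drug has started.
- Section 9.2: "Routine safety and tolerability will be evaluated from the results of reported signs and symptoms, scheduled physical examinations, vital sign measurements", together with laboratory results.

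Section 6.3 also collects, every 3 months for up to 3 years, how long treatment lasted and why it stopped. Section 10.2 does not say how either item will be summarised.

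**The concern.** A safety analysis should account for the serious events a trial has chosen to collect. Here the collection rule ignores causality, while the analysis rule selects on it. An SAE that an investigator attributes to the assigned drug, or to nothing in particular, would be recorded and sent to the DSMC and IRB but would appear in no planned table. The trial's intervention is a recommendation about which drugs to give, so those events are relevant to a reader of the results.

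There are two practical consequences. With 2 to 5 centres and two opposite sentences in Section 14.3.1, sites may capture different sets of AEs. Also, Section 9.1.3 censors patients who change therapy for reasons other than RECIST progression. If toxicity-related discontinuations are not summarised, a reader cannot see how much of that censoring they may explain.

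**Working it through.** The plan gives no safety figure to reproduce. The check compares the passages, counts calendar entries and works out the SAE window.

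**1. SAE collection against SAE analysis.** Section 14.3.2 describes SAEs as adverse events that meet listed criteria, so they are a subset of AEs. Section 10.2.3 restricts AE reporting to biopsy-related events, names no SAE output and carves out no exception. Taken together, an SAE judged unrelated to a biopsy is collected under 14.3.2 and excluded under 10.2.3.

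**2. Whether the SAE window overlaps treatment.** The calendar puts the on-treatment biopsy 4 to 8 weeks after start of therapy. Thirty days is 30/7 = 4.3 weeks. Counting only days after the biopsy, the window across patients runs from week 4 to week 8 + 4.3 = 12.3. The Study Summary places this biopsy at 2 to 4 weeks, which would give week 2 to week 4 + 4.3 = 8.3. Either way the window falls after therapy has started, so drug-related SAEs can be captured for a patient still on treatment. These ranges are envelopes across patients; each patient contributes about 30 days after that biopsy. The baseline window can also overlap treatment, because Section 6.1 lets a new therapy begin while results are awaited.

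**3. Section 14.3.1 against itself and Section 7.** One paragraph collects biopsy-related AEs only and the next collects all AEs; both cannot be followed. The definition also requires onset after study drug has started. The baseline biopsy precedes the report, and the calendar dates start of therapy from the first drug taken after the report is delivered. A complication of the baseline biopsy before any drug therefore falls outside the definition, although it is exactly the kind of event Sections 7 and 10.2.3 mean to report.

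**4. Section 9.2 against the calendar.**

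| Assessment | Scheduled | After guided therapy starts |
|---|---|---|
| Vital signs | Pre-study, after registration | 0 |
| CBC, PT/INR | Pre-study | 0 |
| Physical examination | Pre-study, EOT | 1 (EOT) |

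Study blood tubes are drawn at 4 to 8 weeks, month 9 and EOT, but they are not described as safety tests. Section 9.2 takes its laboratory schedule from the flow chart, so it adds nothing to these counts.

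**5. Size.** The number of omitted SAEs would be (SAEs in the windows) × (proportion judged not biopsy-related). The documents give neither input, so no count can be stated.

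**The case against.** The strongest reply is that the biopsy-only scope is deliberate. Sections 7 and 10.2.3 agree on it, Section 7 gives a reason, and the monitoring plan classes the study as low risk. Section 10.2.3 speaks of AEs without mentioning SAEs, so the specific rule in 14.3.2 could be read as standing beside it. SAEs of any cause still reach the DSMC and IRB. Relatedness judged without blinding is unavoidable in an open-label single-arm trial.

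Most of this stands, and the biopsy-only scope for non-serious AEs can stay. It does not close the gap: sending individual events to a committee is not an analysis rule, and no section says that SAEs will be tabulated.

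A reader might infer more than the documents support:

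- *That unrelated SAEs are lost.* They are missing only from the planned safety summary.
- *That tolerability has no data, or that these SAEs are the only toxicity signal.* Treatment length, reason for discontinuation and an EOT examination are also collected.
- *That the on-label rationale fails.* Section 10.2.1 accepts, for example, "any anti-estrogen plus any MTOR inhibitor in the" exemestane-plus-everolimus group. That wording decides who is evaluable; it does not authorise off-label use. The Background does not say that the other drugs are unapproved.
- *That about 31 of 74 patients are moved off fulvestrant alone with their toxicity unreported.* The arithmetic is 75% − 32.5% = 42.5%, and 0.425 × 74 = 31.45. But the 75% is Section 10.1's construct for a historical control, not what these patients would otherwise receive; the Background lists other second-line options. The figure does not measure omitted SAEs.
- *That the intervention is made to look free of toxicity.* Section 10.2.3 states its scope openly.

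**Conclusion.** The point holds in a limited form and should be corrected before analysis. Read literally, Section 10.2.3 yields an incomplete safety summary, because it excludes SAEs that 14.3.2 collects regardless of cause. Section 14.3.1 contradicts itself, and its AE definition misses baseline-biopsy complications before therapy. The evaluation promised in Section 9.2 is largely, not wholly, unsupported: after guided therapy starts there is one scheduled examination and no scheduled vital signs or safety laboratory tests.

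The size in events is unknown. The PFS estimate is not changed. The conclusion assumes that 10.2.3 would be applied as written, with no separate SAE output planned elsewhere; the documents show none.

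**What to change.** In Section 10.2.3, replace the restricting sentence with:

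> Biopsy-related AEs, and all SAEs collected under 14.3.2 regardless of relationship, will be tabulated by relationship and listed with the regimen received. Discontinuations for toxicity (reason collected under 6.3) will be summarised descriptively. SAE capture covers only 30 days around each biopsy and is not a full toxicity profile.

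A listing by regimen suits the small groups: on the plan's shares, capecitabine would have about 0.10 × 74 = 7 patients.

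In Section 9.2, limit the safety and tolerability text to what the calendar collects. In Section 14.3.1, reconcile the two collection paragraphs and the AE definition with Section 7, so that complications from the baseline biopsy onward count.

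The cost is one or two extra descriptive tables and a safety summary that may look slightly less favourable. No new patient procedures are needed. Because Section 12 restricts data capture, confirm that the case report forms hold the SAEs and the discontinuation reason; Section 6.3 does not describe a toxicity category for that reason.

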## 11 REGISTRATION GUIDELINES

**Patients must meet all of the inclusion and none of the exclusion criteria listed in Section 5 prior to registration.**

**Study related screening procedures can only begin once the patient has signed a research consent form. Patients must not begin protocol treatment prior to registration.**

After informed consent is signed, patient eligibility is determined during the screening period by the study team. When all screening procedures are complete, eligibility must be confirmed by three people, one of whom is an investigator. Once the eligibility review is signed by all three study team members, it is documented in the relevant patient records and the patient study status is changed from screening to treatment in the RedCap. The patient is then registered to this study. No treatment may begin unless this process has occurred.

## 12 DATA SUBMISSION SCHEDULE

The Case Report Forms (CRFs) are a set of (electronic or paper) forms for each patient that provides a record of the data generated according to the protocol. CRF's will be created prior to the study initiation and updated (if applicable) when amendments to the protocol are approved by the respective IRB. **Data capture will be restricted to endpoints and relevant patient information required for planned manuscripts.**

These forms will be completed throughout the study. The medical records will be source of verification of the data. During the study, the CRFs will be monitored for completeness, accuracy, legibility, and attention to detail by a member of the Quality Management Specialist at the Inova Schar Cancer Institute. The CRFs will be completed by a member of the study team as listed on the Delegation of Authority Log. The data will be reviewed no less than annually by the Inova Schar Cancer Institute Data and Safety Monitoring Committee. The Investigator will allow the Data and Safety Monitoring Committee or Research Compliance Office personnel access to the patient source documents, clinical supplies dispensing and storage area, and study documentation for the above-mentioned purpose. The Investigator further agrees to assist the site visitors in their activities.

## 13 SPECIAL INSTRUCTIONS

### 13.1 Biopsy samples

A total of THREE core tumor samples should be collected per patient at each time point (baseline, week 6, optional EOT) using core needle (minimum 18 gauge, preferable 14 gauge)

Tumor samples will be processed per the lab manual. One core sample will be formalin fixed and paraffin embedded for immunohistochemical analysis.

One core sample will be placed in a labeled cryotube containing tissue preservation media and flash frozen in liquid nitrogen for at least 15 minutes and then stored at -70 or -80 degrees.

One core sample will be placed in OCT medium in an OCT cassette. The cassette will then be frozen in liquid nitrogen for 15 minutes and then stored at -70 or -80 degrees.

**13.1.1 Time points**  
Baseline and week 6, optional EOT

**13.1.2 Required Forms**

Each sample collection container (tube, syringe, etc) and storage device (cryotubes, etc) must be minimally labeled with:

- Study name: SPOCK
- Subject ID number: 3 digit site number + 3 digit patient number
- Date of collection
- Time of collection (24-hour clock)
- Sample time point, e.g., Cycle 1 Day 1 PK sample

**Please ensure that the sample information, i.e. date and time of collection, is identical to that captured in source documents.**

## **14 CONSIDERATIONS**

**14.1 Informed consent**

Informed consent will be obtained from all research participants prior to performing any study procedures using the most recent IRB approved version.

**14.2 Institutional Review**

Study will be approved by the Western Institutional Review Board.

**Data and Safety Monitoring Plan**

This study meets the Inova Schar Data Safety and Monitoring Committee (ISCI DSMC) definition for low risk. All low risk studies are audited no less than annually by the ISCI DSMC and audit reports will be reviewed and approved by the full ISCI DSMC. The DSMC will also review all Serious Adverse Events for patients on this study.

#### **14.3 Adverse Events / Serious Adverse Events**

This study will utilize the CTCAE (NCI Common Terminology Criteria for Adverse Events) Version 5.0 for AE and SAE reporting. An electronic copy of the CTCAE Version 5.0 can be downloaded from:

<http://safetyprofiler-ctep.nci.nih.gov/CTC/CTC.aspx>

##### **14.3.1 Adverse Events (AE)**

An adverse event is the appearance or worsening of any undesirable sign, symptom, or medical condition occurring after starting the study drug even if the event is not considered to be related to study drug. For the purposes of this study, the terms toxicity and adverse event are used interchangeably. Medical conditions/diseases present before starting study drug are only considered adverse events if they worsen after starting study drug. Abnormal laboratory values or test results constitute adverse events only if they induce clinical signs or symptoms, are considered clinically significant, or require therapy.

Adverse Events will be collected only if they are related to the study biopsies.

Information about all adverse events, whether volunteered by the subject, discovered by investigator questioning, or detected through physical examination, laboratory test or other means, will be collected and recorded and followed as appropriate.

The occurrence of adverse events should be sought by non-directive questioning of the patient at each visit or phone contact during the study. Adverse events also may be detected when they are volunteered by the patient during or between visits or through physical examination, laboratory test, or other assessments. As far as possible, each adverse event should be evaluated to determine:

1. the severity grade based on CTCAE v.5 (grade 1-5)
2. its relationship to the study procedure (definite, probable, possible, unlikely, not related)
3. its duration (start and end dates or if continuing at final exam)
4. action taken (no action taken; non-drug therapy given; drug-therapy given; hospitalization/prolonged hospitalization)
5. whether it constitutes an SAE

All adverse events will be treated appropriately. Once a related adverse event is detected, it should be followed until its resolution, and assessment should be made at each visit (or more frequently, if necessary) of any changes in severity, the suspected relationship to the study drug, the interventions required to treat it, and the outcome.

All adverse events will be immediately recorded in the patient research chart.

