**Name of Institution**

## STUDY SUMMARY

Title	Systems Biology Guided Therapy for Breast Cancer Positive for Oestrogen Receptor after Aromatase Inhibitor and CDK inhibition.
Short Title	SPOCK
Protocol Identifiers (IRB – internal)	U21-02-4401
IND number	N/A
Phase	II
Design	
Open label, interventional
 
All patients will have a biopsy at the beginning of the trial. The biopsy will be sent for DNA sequencing through FoundationOne (clinical test) and RNA profiling at Fulgent (research test) for determination of activation of various oncogenic pathways and phenotypes. The results will be analyzed by [name] and [name], and a treatment recommendation will be made to the treating physician based on the algorithm below.
 
Biopsies will also be performed 2-4 weeks after the start of therapy for correlative purposes.

Study Duration	24 months recruitment, with up to 3 years of follow up per patient
Objectives	
Primary To determine if systems biology guided therapy can improve PFS
 
Secondary To determine the minimum turn-around time needed for systems biology analysis
 
To determine the response rate to systems biology guided therapy
 
To compare PFS based on concordance with recommended treatment

Number of Subjects	74 treated according to recommendations
Diagnosis and Main Eligibility Criteria	
 
• Metastatic or incurable breast cancer
 
• Progression while on aromatase inhibitor and CDK inhibitor
 

	
 
• Biopsiable lesion
 
• ECOG 0-2
 
• Age 18 or greater
 

Study Product, Dose, Route, Regimen	Drug determined by treating oncologist based on recommendation from systems biology analysis.
Duration of administration	Until intolerance or progression.
Reference therapy	Unguided therapy
Statistical Methodology	The PFS will be compared to 8 months, which is the approximate expected median PFS of fulvestrant +/- alpelisib as second line unguided therapy after AI+CDK inhibitor based on SOLAR-1. With a two-sided alpha of 0.1, beta of 0.2, 18 months of accrual, and 6 months of follow-up, 74 patients are needed to detect a 4 month improvement in PFS with genomic - guided therapy.

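### The AE definition in Section 14.3.1 starts at study drug, so read literally it excludes non-serious baseline-biopsy complications that begin before drug and do not worsen, although biopsy-related AEs are the only AEs to be collected.

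*Combined protocol and SAP*

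**What the plan says.** Section 14.3.1 opens the AE window at study drug: an AE is a new or worsened clinical finding "occurring after starting the study drug even if the event is not considered to be related to study drug". It then repeats that anchor for conditions already present: "Medical conditions/diseases present before starting study drug are only considered adverse events if they worsen after starting study drug".

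The same section limits collection to biopsy events: "Adverse Events will be collected only if they are related to the study biopsies". Section 7 says the same about collection. Section 10.2.3 says the same about reporting and takes all biopsied subjects as the safety population, with no requirement that they have started drug.

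Section 14.3.1 is also inconsistent on relatedness. Its evaluation list asks for "its relationship to the study procedure", while its follow-up rule refers to "the suspected relationship to the study drug".

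For serious events, Section 14.3.2 uses a biopsy anchor: "Information about all serious adverse events within 30 days of a study biopsy will be collected and recorded". One of its hospitalization exceptions nevertheless keeps a drug anchor, for a condition that "has not worsened since the start of study drug".

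**The concern.** The definition is tied to drug, while collection, reporting and the denominator are tied to the biopsy. The two starting points differ for the baseline biopsy, which is the one every patient has before any new treatment. An event must first be an AE before the biopsy-related filter can apply, and that filter narrows the definition without moving its start.

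Two things are at stake. If staff apply the definition as written, the non-serious biopsy AE rate could be biased downward. If the 2-5 centers (Section 4.3) settle the conflict differently, events could be recorded unevenly between them. Apart from serious events, biopsy-related AEs are all the safety data the trial will produce.

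**Working it through.** The plan states no figure on this point and no arithmetic applies. The check is of the order of events and of what each rule captures.

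**Order of events**

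1. Study Summary: "All patients will have a biopsy at the beginning of the trial".
2. Section 6.1: the most recent therapy may run up to the biopsy, and a new therapy may be started after the biopsy while results are awaited.
3. Section 8, footnote 5: start of therapy is the first drug day after the biopsy report reaches the treating oncologist.

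The protocol does not define study drug, and Section 3 (Drug Information) is marked N/A. There are two natural readings:

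- The drug chosen from the systems biology recommendation, as the Study Summary describes the study product. This cannot start before the biopsy result exists.
- Any new drug, including therapy started while waiting. Section 6.1 places this after the biopsy too.

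The second reading can shorten the gap between biopsy and drug, but on both readings the baseline biopsy comes first.

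**What each rule captures, read literally (biopsy-related events)**

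| Event | Appears after drug start | Worsens after drug start | 30-day serious-event rule | Captured |
|---|---|---|---|---|
| Baseline biopsy, non-serious, begins before drug, does not worsen | No | No | No | **No** |
| Baseline biopsy, non-serious, patient never starts drug | No | No | No | **No** |
| Baseline biopsy, non-serious, begins before drug, worsens after | No | Yes | No | Yes |
| Baseline biopsy, non-serious, first appears after drug start | Yes | – | No | Yes |
| Week 6 or optional end-of-treatment biopsy, non-serious, new after drug start | Yes | – | No | Yes |
| Any study biopsy, serious, within 30 days | – | – | Yes | Yes |

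The loss is confined to the first two rows. Patients in the second row still count in the Section 10.2.3 denominator.

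**Size**

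Sizing the loss would need the non-serious complication rate after the baseline biopsy, the interval from biopsy to first new drug, and the number of biopsied patients who never start drug. The documents give none of these, so no estimate is offered.

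**The case against.** The strongest reply is that the protocol, read as a whole, already makes its intent clear. Sections 7, 10.2.3 and 14.3.1 all direct attention to biopsy-related events, and Section 14.3.2 runs its serious-event window from the biopsy. An event related to a biopsy cannot precede it, so the relatedness filter implies its own start, and a trial-specific rule would normally prevail over a generic definition. Because study drug is undefined, the text could also be called ambiguous rather than exclusionary. Finally, serious events include those judged medically significant and must be reported whether or not they are related, so the complications of most concern are captured.

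Much of this stands. The intent is plain, many sites would probably record these events anyway, and both the downward bias and the uneven collection are possibilities, not demonstrated effects. It is also fair to call this an internal inconsistency in a definition rather than a flaw in an analysis method. The mixed relatedness wording and the hospitalization exception do not themselves cause the loss of non-serious events; they are further signs of incomplete conversion from a drug-trial template.

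The conflict nevertheless remains. The drug anchor appears twice in the definition, the second time as an explicit rule that earlier conditions count only on worsening, and nothing in the protocol says that the biopsy-related sentence overrides it. The undefined term does not help, since either natural reading puts study drug after the baseline biopsy.

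**Conclusion.** The concern holds and is minor. As written, the AE definition excludes non-serious baseline-biopsy complications that begin before drug and do not worsen, and it leaves biopsied patients who never start drug unable to contribute a non-serious AE. This rests on a literal reading of Section 14.3.1 and on study drug meaning a drug started after the baseline biopsy, as the Study Summary and Sections 6.1 and 8 indicate.

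Confidence is high about the conflict in wording. The practical effect is unknown, because it depends on how sites apply the text. The affected output is a descriptive safety summary; PFS, ORR, sample size and power do not change.

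**What to change.** Reconcile the passages on the biopsy anchor that the protocol already uses elsewhere:

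- In Section 14.3.1, define an AE by onset or worsening from the start of any study biopsy (baseline, week 6 or optional end of treatment), whether or not drug has been started. Keep the existing limit to biopsy-related events.
- Use the same biopsy anchor in the pre-existing-condition sentence, in place of both references to study drug.
- In the follow-up rule, assess relationship to the study procedure, the term already used in the evaluation list.
- In Section 14.3.2, bring the drug-start phrase in the hospitalization exception into line with the same anchor.

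This does not require an end date for non-serious AEs; the documents set none, and none is proposed here. The cost is a protocol wording amendment and any matching data-collection text (the case report forms are not in the documents). Sample size and efficacy analyses are unaffected.
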